### **8.1 Eligibility Criteria**

Principal investigator will approach those who are eligible, inform and ask for consent from caregivers and also assent from children when possible. The purpose of this approach is to avoid selection bias and improve the sample's relevance in the clinical environment.

Participants must meet the following **inclusion criteria**:

- Children who can read and communicate in Chinese
- Aged 6 to 12 years old (school-aged children).
- Diagnosed with cancer and currently undergoing active treatment.
- Identified as experiencing sleep disturbances, defined by a Chinese Pittsburgh Sleep Quality Index (PSQI) global score of  $\geq 5$ .

The following **exclusion criteria** will apply:

- Diagnosed with hematological diseases unrelated to cancer (e.g., sickle cell anemia, thalassemia).
- Presence of severe cognitive impairment, which may hinder the ability to follow instructions or engage with intervention components.

These criteria are designed to select participants who are both clinically relevant and developmentally capable of participating in the intervention and completing required assessments.

## **8.2 Sample Size Planning**

As this is a pilot feasibility study, the sample size is determined based on guidelines for evaluating preliminary interventions rather than hypothesis testing. According to Teresi et al. (2022), a minimum of 30 participants per group is generally sufficient for feasibility trials. To accommodate an estimated 10% attrition rate at the four-week post-intervention assessment, a total sample of 68 participants will be recruited, with 34 allocated to each group. An initial target of 10 participants (and their parents/legal guardians) from the intervention group will be invited for semi-structured interview for process evaluation. The analysis will continue until data saturation is achieved.

## **9. Description of the Evidence-Based Protocol**

The Dreamcatchers Programme is a multi-component intervention, focusing on sleep hygiene education, PMR, and breathing exercises, is designed to address sleep disturbances in pediatric oncology patients through non-pharmacological approach. The programme is simple, feasible, and can be adapted to both hospital and home settings. It also involves a structured education, practice, and follow-up approach to make sure patients and caregivers are consistently able to put the intervention into play.

### **9.1. Sleep Hygiene Education**

The first part of the intervention consists of a group education session on sleep hygiene for pediatric oncology patients and their caregivers. Each session will accommodate a maximum of 10 participants and will last approximately 45 minutes as informed by (2019), Sriasih et al. (2019), and Zupanec et al. (2017), facilitated by

a nurse using a PowerPoint presentation. The session will begin with highlighting how sleep contributes to recovery and general well-being. Next, strategies for creating an optimal sleep environment will be covered, including controlling lighting and noise that may disrupt sleep. The importance of establishing a consistent bedtime routine will be stressed, reminding them to maintain these practices at hospital or at home.

Suggestions of screen-free activities, along with alternative activities to engage children without interfering with their sleep will be discussed. Caregivers will learn techniques of diaphragmatic breathing and PMR to promote relaxation, further aiding sleep improvement.

Finally, patients and caregivers will learn how to complete the sleep diary so they can monitor children's sleep habits, how much they sleep, and whether they perform the recommended exercises. They will get the sleep diary as a booklet that covers the summary of what makes for positive sleep habits. The resource can assist caregivers and health professionals as a useful tool in seeing the progress made and helping improve sleep for young cancer patients. Patients and caregivers will be reminded to bring the sleep diary to follow-up appointments for review and data collection.

## **9.2. Progressive Muscle Relaxation (PMR)**

Following the education session, practical demonstrations of PMR and breathing exercises will be conducted, allowing patients and caregivers to practice what they have learned. These exercises will be designed to be simple, age-appropriate, and easily integrated into daily routines.

Despite previous studies show that the effectiveness of PMR is not always high, the Dreamcatchers Programme includes PMR as it is seen as manageable for improving sleep time and quality (Khoirunnisa et al., 2019; Sulistyawati et al., 2021; Zupanec et al., 2017). PMR helps lower stress and anxiety by modulating the activities of the autonomic nervous system (Sari et al., 2024). The gentle movements in PMR make it possible for patients with less strength or mobility, as opposed to doing stretches, which might be difficult because of related issues like pain or weakness. PMR's simplicity ensures high adherence and ease of implementation in clinical or home

settings, aligning with the feasibility focus of a pilot study. Although stretching exercises are beneficial for physical health, there is insufficient evidence demonstrating stretching being able to improve sleep quality or address the psychological factors prevalent in this fragile population. The entire PMR routine will take approximately 10-15 minutes, consistent with the duration of relaxation exercises noted in earlier research.

### **9.3. Breathing Exercises**

Breathing exercises will also be demonstrated and advised to be used before bedtime, aiming to reduce physiological arousal and promote relaxation through slowing down breathing rate, amplifying vagus nerve activity and normalizing stress responses (Chen et al., 2016; Chui et al., 2021). This intervention will specifically utilize diaphragmatic breathing control exercises, which are shown to enhance tidal volume and regulate breathing patterns (Zaccaro et al., 2018). The breathing routine, incorporating box breathing techniques, will last 5-10 minutes and is to be practiced as part of the children's wind-down routine before sleep (Murphy, 2019).

To support consistent practice, a video recording of the PMR and breathing exercises will be provided via QR code with reference to Student Health Service's (2016) materials, integrated into the sleep diaries for easy reference by patients and caregivers.

The participants will be supported after the first introductory session through weekly follow-up sessions for four weeks. These sessions are meant to repeat and practice the techniques learnt, solve any doubts, and monitor participants' sleep hygiene practices. Regular check-ups help to maintain contact and offer support to everyone involved in the treatment.

Nurses will play a key role in delivering sleep hygiene education, demonstrating exercises to patients and caregivers, and conducting follow-up sessions. The principal investigator will train nurses covering sleep hygiene principles, techniques of breathing and PMR exercises, instructions on charting the sleep diary. Trained nurses will conduct mock demonstrations of the group education session and individual exercise demonstrations with their peers. The entire training programme

will take around one week before the actual implementation of the intervention. Trained nursing staff then lead the group education session covering sleep hygiene principles, techniques of breathing and PMR exercises.

## **10. Data Collection Methods and Procedures**

Data collection for this pilot RCT will occur at three time points: baseline (T0), immediate post-intervention (T1), and a 3-month follow-up (T2). A summary table of intervention and data collection methods and procedures is included in Appendix II.

### **10.1 Participant Recruitment**

Participants will be recruited at ambulatory chemotherapy day centers at HKCH. Trained personnels will approach eligible families, provide study details, and obtain informed consent from parents/legal guardians as well as child assent when appropriate. After consent is obtained, participants will be randomly assigned to either the intervention group or the waitlist control group using a concealed block randomization method, managed by an independent researcher to minimize bias.

### **10.2 Baseline Assessment (T0)**

At enrollment, all participants will complete the following assessments: demographic survey for data on age, gender, cancer type, and treatment phase, Chinese version of the PSQI for evaluating subjective sleep quality, Chinese PedsQL Cancer Module 3.0 for assessing quality of life, and sleep diary to track sleep patterns and exercise frequency (only for intervention group).

### **10.3 Post-intervention Assessment (T1)**

Immediately following the four-week intervention period, all participants will undergo repeat assessments identical to those performed at T0, including Chinese PSQI, Chinese PedsQL Cancer Module 3.0, and sleep diary review.

In addition, participants in the intervention group will complete a satisfaction survey and semi-structured interview with both quantitative Likert-scale items and open-ended questions.

#### **10.4 Three-month Follow-up (T2)**

To assess the durability of the intervention effects, participants will complete a third round of assessments, including Chinese PSQI, Chinese PedsQL Cancer Module 3.0 and sleep diary review.

#### **10.5 Data Integrity and Confidentiality**

All research data will comply with Hospital Authority policies on the handling, storage, and destruction of medical records. Data collected, including demographic information and assessments (e.g., Chinese version of the PSQI and PedsQL Cancer Module 3.0), will be de-identified using unique participant codes instead of names. These codes will be stored separately in a password-protected electronic file accessible only to authorized personnel. Physical records, such as consent forms, will be securely locked in a ward manager's office at HKCH. Electronic data will be stored on an encrypted, institution-approved server to safeguard protected health information. Access will be restricted to the principal investigator and trained research staff, with no identifiable information disclosed in publications.

Data will be retained for five years post-study and then securely destroyed, with paper records shredded and electronic files permanently deleted. In the event of incidental findings, such as severe sleep disturbances, the research team will notify the participant's parents and medical team while keeping confidentiality.

### **11. Instruments**

A combination of subjective instruments will be used in this study to capture a comprehensive understanding of the participants' sleep quality and overall well-being. The selected tools have been validated for use in pediatric populations and adapted for Chinese children. The authors of the Chinese versions of the PSQI and the PedsQL Cancer Module 3.0 have been contacted and have provided these instruments for use in this study.

The decision to utilize subjective measures rather than objective tools like wrist actigraphy, which focuses on what patients feel and experience, and offers more practical and suitable ways to meet the special requirements of this group. Objective

tools like wrist actigraphy, require wearing devices for a period that may cause discomfort or anxiety, especially for those with medical devices or skin sensitivities. Young children might remove these devices during sleep or play, leading to incomplete data. It is not necessary to spend significant resources on logistics and finances for actigraphy in a pilot study. Alternatively, sleep diaries and the PSQI provide insights into the pattern and quality of participant's sleep. The reliability, validity, and feasibility of each instrument have been carefully considered to minimize participant burden while maximizing data quality.

### **11.1 Chinese Version of the PSQI**

The PSQI is used broadly to assess subjective sleep quality for the past month. There are seven components in the tool (including sleep latency, disturbances, and duration) that result in a global score of 0 to 21, with higher numbers reflecting worse sleep quality. The Chinese version has been validated for use among Chinese pediatric oncology populations, with Ho et al. (2021) reporting a Cronbach's alpha of 0.71, indicating acceptable internal consistency. The same study reported an intraclass correlation coefficient of 0.90, reflecting excellent test-retest reliability. There is strong agreement between the results from this tool and results from actigraphy.

### **11.2 Chinese Version of the PedsQL Cancer Module 3.0**

The Chinese PedsQL Cancer Module 3.0 allows the measurement of quality of life in cancer children aged 2-18, examining issues such as pain, fatigue, and cognitive problems. Better health-related quality of life is indicated by a high score. Lau et.al. (2010) found that the overall score had high internal consistency with Cronbach's alpha of 0.87 among Chinese pediatric oncology patients. Study by Li et al. (2013) supported the construct validity of the Chinese version, as a strong positive link between children's self-esteem and quality of life ( $r = 0.50$ ) and a strong negative correlation between treatment-related symptoms and quality of life ( $r = -0.65$ ) was recorded.

### **11.3 Sleep Diary**

Participants will be asked to complete the sleep diary throughout the study period. It tracks bedtime, wake time, perceived sleep quality, and specific for intervention

group – adherence to PMR and breathing exercises, while also including QR codes that link to instructional videos. While the sleep diary is not validated psychometrically, it helps capture real-life behaviors and participant's adherence to the programme.

#### **11.4 Satisfaction Survey**

The satisfaction survey is custom-designed that combines Likert-scale items and open-ended questions to assess the acceptability, usability, and perceived benefits of the Dreamcatchers Programme, only to intervention group at T1. The content includes items that evaluate the clarity of educational material, ease of performing exercises, and overall satisfaction with the programme. Quantitative responses will be analyzed descriptively, while qualitative responses will undergo thematic coding to identify common feedback patterns that can inform future refinements.

#### **11.5 Semi-structured Interview**

Supplementing the satisfaction survey, a semi-structured interview will be conducted with an interview guide provided for process evaluation. A total of 10 participants and their parents or legal guardians from the intervention will be invited for the interview. However, the final sample size will depend on the data saturation. An in-depth, one-on-one, audiotaped, semi-structured interview will be conducted with the 10 participants and their parents or legal guardians.

### **12. Data Analysis**

The data analysis will evaluate the intervention's impact on sleep quality, duration, quality of life, as well as its feasibility and acceptability, comparing results against baseline measurements. For the Chinese PSQI, global and component scores will be compared between groups at T1 and T2 using independent t-tests, while repeated-measures ANOVA will assess group-by-time effects, specifically focusing on changes in subjective sleep quality from baseline to T1 and T2 to assess the intervention's impact over time.

Regarding the Chinese PedsQL Cancer Module 3.0, total and subscale scores will be compared to baseline and between groups at T1 and T2 using independent t-tests, with

repeated-measures ANOVA evaluating group-by-time effects for quality-of-life improvements. Descriptive statistics will summarize adherence rates, intervention practice frequency for the intervention group, confirming protocol fidelity.

For the satisfaction survey, quantitative analysis will involve calculating mean Likert scores per question, such as ease of understanding, usability, while qualitative analysis will use thematic coding of open-ended responses to identify common feedback themes, such as preferred components, for programme refinement.

This comprehensive analysis aims to assess acceptability, feasibility, and areas for programme refinement, using baseline comparisons to gauge intervention effectiveness. The qualitative data analysis process will begin immediately after each interview, following the thematic analysis framework introduced by Braun and Clarke (2006).

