## 7. Study Design

This study is structured as a pilot prospective and randomized controlled trial (RCT) with a 1:1 allocation to either the intervention group or waitlist control group. The intervention group will receive the Dreamcatchers Programme, including sleep hygiene education, PMR, and breathing control exercises, which will be delivered over 4 weeks with weekly in-person follow-ups. The waitlist control group will continue to receive routine hospital support and pediatric oncology health information (e.g., neutropenic diet tips) to maintain engagement without sleep-specific strategies. The trial will span 4 weeks, followed by a 3-month follow-up to assess the sustainability of outcomes.

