## Appendix II - Intervention and Data Collection Methods and Procedures

Stage	Description	Assessments/Activities	Participants	Notes
Recruitment and Consent	Recruitment occurs at ambulatory chemotherapy day centers at HKCH. Trained research nurses approach eligible families, provide study details, and obtain informed consent from caregivers and child assent when appropriate.	None	All eligible participants	Consent and assent obtained prior to randomization.
Randomization and Allocation	Participants are randomly assigned to intervention or waitlist control group using concealed block randomization managed by an independent researcher to minimize bias.	None	All participants	Ensures balanced group allocation; performed after consent.
Baseline Assessment (T0)	Conducted at enrollment to establish baseline measures. Assessments include: 
 
Demographic survey (age, gender, cancer type, treatment phase)
 
Chinese PSQI (subjective sleep quality)
 
Chinese PedsQL Cancer Module 3.0 (quality of life)
 
	Demographic survey, Chinese PSQI, Chinese PedsQL Cancer Module v3.0	All participants	Performed after randomization.
Intervention Group: Introductory Session	A total of 60 mins nurse-led group session at education room at HKCH introduces the intervention for up to 10 children and caregivers. includes: 
 
45 mins sleep hygiene education (role of sleep, optimizing sleep environment, addressing poor sleep habits)
 
Demonstration of box-breathing (4-4-4 cycle, 5–10 mins nightly)
 
Demonstration of PMR (tensing/relaxing muscle groups, 10–15 mins nightly)
 
	Sleep diary distribution (intervention group)	Intervention group only	Child-friendly instructions (e.g., “squeeze a lemon” for PMR) ensure engagement.

	
 
• Distribution of sleep diaries with QR code videos for home practice
 
			
Weekly Follow-Ups (Weeks 1–3)	
Weekly in-person sessions at the Integrated Rehabilitation Center reinforce intervention techniques. Nurses:
 
 
• Re-demonstrate box-breathing and PMR
 
• Review sleep diaries to check adherence to nightly practice
 
• Address challenges and clarify techniques
 
	Sleep diary review (intervention group)	Intervention group only	Ensures fidelity and supports adherence. Control group receives general health education to prevent contamination.

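### The intervention arm is taught in groups, but Section 12 treats all children as independent; if outcomes correlate within a session, standard errors are too small

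*Protocol*

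**What the plan says.** Section 7 describes a trial "with a 1:1 allocation to either the intervention group or waitlist control group", and Section 10.1 has participants assigned after consent, so the unit of randomisation is the child.

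Delivery in the intervention arm starts in groups. Section 9.1: "The first part of the intervention consists of a group education session on sleep hygiene for pediatric oncology patients and their caregivers". The same section puts a cap of 10 on the size of these groups. Appendix II describes a "nurse-led group session at education room at HKCH introduces the intervention for up to 10 children and caregivers" and lists the PMR and breathing demonstrations within the same 60 minutes. Later contact is described as "Weekly in-person sessions at the Integrated Rehabilitation Center reinforce intervention techniques", without saying whether these are run in groups or child by child.

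For controls, Section 7 says: "The waitlist control group will continue to receive routine hospital support and pediatric oncology health information". No group session is described for them.

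For the PSQI, Section 12 states that "global and component scores will be compared between groups at T1 and T2 using independent t-tests", with repeated-measures ANOVA for the group-by-time effect. The PedsQL is handled with the same two methods. Neither has a term for session or nurse.

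**The concern.** Individual randomisation with group delivery in one arm is a partially nested design. Children who share a room, a nurse and a discussion may end up more alike than children who do not. An independent t-test does not allow for that. The repeated-measures ANOVA allows for correlation within a child over time, but not between children taught together.

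Any positive within-session correlation inflates the true variance of the intervention-arm mean. The planned tests miss this inflation, so intervals are too narrow and the false-positive rate exceeds its nominal level, for PSQI and PedsQL at both T1 and T2.

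The pilot label does not make this irrelevant. Section 5 hypothesises a significant improvement over control, and Section 15 says that positive results would demonstrate efficacy. Nor is this only a matter left to a later analysis plan, since the protocol itself names the tests.

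**Working it through.** **The plan's own figure.** Section 8.2 takes 30 per group and allows for 10% attrition: 30 / (1 − 0.10) = 33.3, rounded up to 34 per arm, 68 in total. This reproduces and is not in dispute.

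**Inputs from the protocol.** 34 children in the intervention arm (Section 8.2) and at most 10 per session (Section 9.1, Appendix II). 34 / 10 = 3.4, so at least 4 sessions, with a mean size m = 34 / 4 = 8.5.

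**Assumptions.** The protocol gives neither an ICC nor a significance level. I take ICCs of 0.01 to 0.10, a two-sided 5% level, equal variances in the two arms and no clustering among controls.

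**Formulas.**
- Design effect in the intervention arm: DE = 1 + (m − 1) × ICC. In the control arm it is 1.
- With equal arms, true variance of the difference divided by the variance assumed: V = (DE + 1) / 2.
- Type I error of the planned test: 2 × [1 − Φ(1.96 / √V)].

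**Results for 4 sessions, m = 8.5.**

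| ICC | DE | V | √V | Type I error |
|---|---|---|---|---|
| 0.01 | 1.075 | 1.0375 | 1.019 | 5.4% |
| 0.02 | 1.150 | 1.0750 | 1.037 | 5.9% |
| 0.05 | 1.375 | 1.1875 | 1.090 | 7.2% |
| 0.10 | 1.750 | 1.3750 | 1.173 | 9.5% |

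A correct interval would therefore be about 4%, 9% and 17% wider at ICCs of 0.02, 0.05 and 0.10.

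**Check by simulation** (20,000 trials per setting; sessions of 9, 9, 8 and 8 against 34 controls; within-child correlation over time assumed to be 0.5 for the ANOVA):

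| ICC | t-test | Group-by-time ANOVA |
|---|---|---|
| 0 | 4.8% | 4.9% |
| 0.01 | 5.1% | 5.2% |
| 0.02 | 5.8% | 5.5% |
| 0.05 | 7.1% | 7.6% |
| 0.10 | 9.6% | 9.7% |

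Both planned tests are affected. At zero correlation both hold their level, so the excess comes from the clustering.

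**Sensitivity to session size.**
- Seven sessions (34 / 7 = 4.86 children each, roughly what follows if the cap of 10 counts caregivers too): 5.2%, 5.4%, 6.1% and 7.3% at ICCs of 0.01, 0.02, 0.05 and 0.10.
- Four sessions with 30 evaluable children per arm (m = 7.5): 5.4%, 5.8%, 6.9% and 8.9%.
- Three full sessions of 10 with 30 evaluable per arm, the least favourable case: 5.5%, 6.0%, 7.7% and 10.4%.

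**Can the trial estimate the ICC itself?** In a balanced one-way analysis of 34 children in 4 sessions, the estimated session variance is zero or negative when F(3, 30) falls below 1 / [1 + m × ICC / (1 − ICC)]. This happens in about 52%, 44% and 32% of trials at true ICCs of 0.02, 0.05 and 0.10. In those trials a mixed model falls back essentially on the unadjusted analysis.

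**The case against.** The strongest reply is that the correlation may be very low. Only one 60-minute session is explicitly a group session. After it come nightly practice at home and follow-ups whose format is not stated and whose content (diary review, individual difficulties) is specific to the child. The PSQI covers the past month and is taken at the end of the four weeks and three months after that. In describing nurse training, Section 9.3 even mentions individual exercise demonstrations, so it is not certain that the exercises are always shown to a whole group. Ten is also a cap, and smaller sessions shrink the effect. All of this stands. It limits the size of the problem, but not its direction.

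A reader might infer that the standard errors and p-values will in fact be too small. The protocol does not support that: it needs a positive ICC, and none is given. At 0.01 the effect is negligible.

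A reader might also take it as settled that controls are never grouped. The protocol only describes no group session for them; Section 7.3 refers to control-group activities and Appendix II to general health education, with no format given. Grouped controls could add clustering in the second arm. That would not remove the problem, but a model treating controls as ungrouped would then be wrong.

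Finally, the sample size rests on pilot guidance and not on hypothesis testing, so no confirmatory decision turns on a few points of type I error. That is fair, and it is a reason for a light remedy.

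**Conclusion.** The point holds in conditional form. Delivery is grouped in the intervention arm, the tests named in Section 12 assume independence, and any positive within-session correlation makes them anti-conservative. With 4 sessions the type I error runs from about 5.4% at an ICC of 0.01 to 9.5% at 0.10; with 7 sessions, from about 5.2% to 7.3%. These figures rest on assumed ICCs, a 5% level and ungrouped controls. The low end is plausible, given a single stated group session and home practice.

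Two stronger conclusions do not follow. The total of 68 is not invalidated, because it was not derived from a power calculation. Nor must the planned tests give way to a mixed model: about 4 sessions are too few to estimate the ICC reliably, so such a model would often make no correction at all. This is an inexpensive improvement, not a flaw that undermines the trial.

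**What to change.** 1. Record the session number and lead nurse for each intervention child, and for controls too if any control activity is run in groups. This has to be in place before the first session, since it may not be recoverable later.
2. Add to Section 12 that, beside the planned tests, the arm difference in PSQI and PedsQL at T1 and T2 is reported with confidence intervals adjusted for within-session correlation at fixed ICCs of 0.02, 0.05 and 0.10. The intervention-arm variance is multiplied by 1 + (m − 1) × ICC, with m taken from the sessions actually held. This needs no estimate of the ICC.
3. State that p-values are read as exploratory.
4. Optionally, show as supportive a partially nested mixed model with a random session effect in the intervention arm and small-sample degrees of freedom (Satterthwaite or Kenward-Roger), noting that its ICC estimate will be very imprecise.

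The cost is two data fields, a few lines of text and somewhat wider intervals in the adjusted report. No additional children or visits are needed.

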## 2. Secondary Hypothesis:

The intervention will enhance quality of life in patients undergoing active cancer treatment compared to the control group, as assessed by the Chinese PedsQL Cancer Module 3.0 at T1 and T2.

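### PedsQL change from baseline is, as worded, tested with independent t-tests on the same children, and neither planned between-group analysis of PSQI or PedsQL adjusts for the baseline score

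*Protocol*

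**What the plan says.** Section 12 (Data Analysis) names two analyses for each instrument.

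- **PSQI:** "global and component scores will be compared between groups at T1 and T2 using independent t-tests", plus a repeated-measures ANOVA for the group-by-time effect.
- **PedsQL Cancer Module:** "total and subscale scores will be compared to baseline and between groups at T1 and T2 using independent t-tests", again with a repeated-measures ANOVA for group by time.

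The document names no paired test and no baseline covariate.

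The scores are repeated measurements on the same children. Section 10.2 says "At enrollment, all participants will complete the following assessments", Section 10.3 says "all participants will undergo repeat assessments identical to those performed at T0", and Section 10.4 says "participants will complete a third round of assessments". The secondary hypothesis in Section 5 is a between-group one: quality of life is "compared to the control group, as assessed by the Chinese PedsQL Cancer Module 3.0 at T1 and T2".

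Three other places bear on the point. Entry requires a PSQI score (Section 8.1: "Identified as experiencing sleep disturbances, defined by a Chinese Pittsburgh Sleep Quality Index (PSQI) global score of" 5 or more). Section 7.2 states that families cannot be blinded. Appendix II places the T0 assessment after randomization.

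**The concern.** There are two separate matters.

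**The PedsQL comparison with baseline.** One named test governs both comparisons in the sentence. For the comparison with baseline the data are paired, so an independent t-test uses the wrong standard error. With positive correlation that error is too large. The test then rejects too rarely and loses power for the 5-point PedsQL improvement named in Section 15. The PSQI sentence does not have this fault.

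**The between-group comparison of both instruments.** The follow-up t-test discards T0, and the ANOVA contrast amounts to comparing changes. Which of the two is more precise depends on r, which is not known in advance: the follow-up score is better below r = 0.5 and the change above it. Adjusting for T0 removes that dependence and uses data already collected from everyone. The protocol also does not say which of its two between-group tests counts if they disagree. In a pilot of about 30 per arm, precision is scarce.

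**Working it through.** **The plan's own figure.** Section 8.2 gives 30 evaluable per arm and 10% attrition: 30/0.9 = 33.3, rounded up to 34, and 2 × 34 = 68. This reproduces, and nothing below changes it.

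**Assumptions.** The protocol gives neither SDs nor correlations between visits. I take n = 30 per arm, equal SDs at each visit, two-sided 5%, and r = 0.3, 0.5, 0.7, 0.9. The top value echoes Section 11.1 ("The same study reported an intraclass correlation coefficient of 0.90"), which is a test-retest figure and not a T0-to-T1 correlation.

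**1. PedsQL against baseline.** The independent test assumes variance 2·SD²/n. The true variance of the mean change is 2·SD²(1−r)/n. The standard error is therefore too large by 1/√(1−r). True error (200,000 simulated trials) and power for a 5-point change (40,000 per cell) are:

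| r | SE ratio | True error | Power, SD 10: as written v paired | SD 15 | SD 18 |
|---|---|---|---|---|---|
| 0.3 | 1.20 | 2.1% | 47 v 61% | 21 v 32% | 14 v 24% |
| 0.5 | 1.41 | 0.6% | 47 v 75% | 17 v 43% | 10 v 31% |
| 0.7 | 1.83 | 0.07% | 47 v 93% | 12 v 62% | 6 v 48% |
| 0.9 | 3.16 | none seen | 45 v 100% | 4 v 98% | 1 v 91% |

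The paired test holds 5% throughout. At low r it also often misses, because the pilot is small.

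**2. Between-group precision.** Set the variance of the follow-up t-test to 1. The change contrast then has 2(1−r). ANCOVA has 1−r², times a small-sample factor 1 + 1/(2n−4) = 57/56.

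| r | Change | ANCOVA | ANCOVA × 57/56 | Below the better planned analysis by |
|---|---|---|---|---|
| 0.3 | 1.40 | 0.91 | 0.926 | 7% |
| 0.5 | 1.00 | 0.75 | 0.763 | 24% |
| 0.7 | 0.60 | 0.51 | 0.519 | 13% |
| 0.9 | 0.20 | 0.19 | 0.193 | 3% |

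With the factor included, ANCOVA beats the follow-up score when r > √(1−56/57) = 0.13 and beats the change when r < 2·56/57 − 1 = 0.96.

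**3. Effect of the PSQI entry cut-off.** Suppose T0 is the screening score and the cut-off sits at the unselected mean. The T0 variance then shrinks by the factor k = 1 − 2/π = 0.363. The follow-up variance becomes 1 − r² + r²k, and r falls to 0.19, 0.33, 0.51, 0.78. Relative variances are 1.15, 1.00, 0.79, 0.40 for change and 0.98, 0.91, 0.75, 0.40 for ANCOVA. The gain over the better planned analysis is then about 2%, 9%, 4% and 0%. No such cut-off applies to the PedsQL.

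**4. PSQI confidence intervals.** The half-width is t × SD × √(2/30) × √(relative variance), with 58 df (57 for ANCOVA). At r = 0.5, follow-up score or change v ANCOVA with the 57/56 factor:

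- SD 2: 1.03 v 0.90
- SD 3: 1.55 v 1.36
- SD 4: 2.07 v 1.81

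Under the cut-off scenario the SD 3 comparison is 1.55 v 1.55 × √0.91 = 1.48.

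**5. Disagreement of the two planned tests.** Take a true 2-point PSQI effect at T1 and T2, the aim in Section 15, with equal correlation between visits and 20,000 simulated trials per cell. The T1 t-test and the three-visit group-by-time F test differ on significance in 3–10% of trials at SD 2, 14–26% at SD 2.5, 28–37% at SD 3 and 40–52% at SD 4. With no effect, each test rejects in 4.8–5.4% of trials, so both are valid.

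**6. Bias if T0 is taken after allocation.** A shift d at T0 in one arm biases the follow-up t-test by 0, ANCOVA by r·d and the change contrast by d. For d = 1 PSQI point, ANCOVA is biased by 0.3 to 0.9 points over r = 0.3 to 0.9, and the change contrast by 1.0.

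**The case against.** **The PedsQL sentence may be loose wording.** It could mean that change from baseline is compared between groups, for which an independent t-test is valid, and the same sentence also names a repeated-measures ANOVA. That reading is possible, so the error figures hold only if the text is followed literally. The sentence still has to be reworded, because it does not say this. Section 15 also does not say that the 5-point aim is a within-arm test, so the power figures illustrate the loss rather than describe a planned test.

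**Baseline adjustment is a preference, and covariates are usually left to the analysis plan.** The between-group t-tests are indeed valid. But the protocol itself names the tests, so the choice has been made there and not deferred.

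**The gain on the primary outcome may be small.** This stands: 0–9% under the cut-off scenario. It does not apply to the PedsQL.

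**Keeping supportive tests leaves room for disagreement.** True: at SD 3 and r = 0.5, ANCOVA differs from the t-test in about 15% of trials and from the F test in about 21%. The two planned tests also answer different questions, one visit against three. What the fix settles is which result is the main one.

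**ANCOVA is exposed to bias if T0 follows allocation in unblinded families.** This is the one real hazard, and the follow-up t-test is immune to it. It is why the fix includes the timing of T0.

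**The sample was not sized for hypothesis tests.** Section 8.2 says so, yet Section 5 hypothesises a significant improvement against control.

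**Conclusion.** The point holds in both parts and should be fixed, but it does not invalidate the plan.

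1. Followed as written, the PedsQL test against baseline is wrong in the conservative direction. It affects a secondary within-group comparison only.
2. The planned between-group analyses are valid but leave precision unused. The gain against the better of the two is largest near r = 0.5 and small at high r.

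The relative variances depend only on the assumed r and n = 30 per arm. The power, interval and disagreement figures also rest on assumed SDs, and the disagreement rate is especially sensitive to the PSQI SD.

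**What to change.** In Section 12:

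- Remove the comparison with baseline from the PedsQL independent t-test sentence, or report within-group change descriptively as a mean paired difference with 95% CI.
- Make the T0-adjusted group difference at T1 and at T2, with 95% CI, the main between-group estimate for PSQI and PedsQL. This can be ANCOVA, or a mixed model of T1 and T2 with T0 as covariate. Keep the t-tests and repeated-measures ANOVA as supportive.
- Optionally, state that the section's reference to baseline comparisons means the baseline-adjusted between-group difference.

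In Appendix II, have T0 completed after consent and before allocation is revealed. Eligibility already needs a PSQI score, so a PSQI taken before allocation can serve as the covariate; the PedsQL would have to be completed at the same point. If this is not possible, keep the unadjusted follow-up comparison as a sensitivity analysis.

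The cost is a rewording of Section 12 and one Appendix II cell, slightly more analysis work, and a change in the order of enrolment steps. No new data, visits or patients are needed, and the total of 68 stands.
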